4.9.6 Determination of Sample Size

The sample size was based on a Kaplan Meier analysis with proportion of patients relapse free at 12 months as the primary endpoint. Assuming a relapse-free proportion of 0.80 at 12 months, 45 patients are required to say that the relapse free proportion is no lower than 0.68, with 95% confidence. To account for 10% attrition, a total of 50 patients are needed.

4.10 DATA QUALITY ASSURANCE

Accurate, consistent, and reliable data will be ensured through the use of standard practices and procedures.

5. REPORTING OF ADVERSE EVENTS

An AE is an unfavorable unintended sign, symptom, or disease that is experienced by the patient, whether or not there is a causal relationship with OCR. At the time of consenting, each patient will be given the names and telephone numbers of the study personnel for reporting AE's. The investigator must conduct thorough assessment to determine the severity of the AE and the relationship to the study drug. Any clinically significant AE of severity moderate or higher, requires follow up until resolution or stabilization by the treating investigator beyond the end of study contact.

All AEs should be recorded in the patient's AE case report form regardless of severity or relationship to the study drug. The investigator must review the laboratory findings for significance (all out of range values must be assessed as clinically significant or not clinically significant) and sign and date the laboratory report. All clinically significant laboratory findings must be reported as adverse events.

Any severe laboratory abnormalities that are considered serious should be reported to the coordinating center as outlined below.

All SAEs must be reported by the investigator to Genentech by email [contact] or [contact] and Providence Regional Research Regulatory Office by email [contact] (Regulatory) and CC [contact] (Study Manager) or fax to [contact] (Regulatory) and [contact] (Study Manager) within 24 hours of the investigator's knowledge of the event.

Severity

The intensity of severity of an AE will be graded as follows:

Mild	Symptoms(s) barely noticeable to subject or does not make subject uncomfortable; does not influence performance or functioning; prescription drug not ordinarily needed for relief of symptoms(s) but may be given because of personality of subject
Moderate	Symptom(s) of a sufficient severity to make subject uncomfortable; performance of daily activity is influenced; subject is able to continue in study; treatment for symptom(s) may be needed.
Severe	Symptom(s) cause severe discomfort; symptoms cause incapacitation or significant impact on subject's daily life; severity may cause cessation of treatment with investigational drug; treatment for symptom(s) may be given and/or subject hospitalized.

Relationship to Study Drug

The relationship or association of the AE to a study drug will be characterized as follows:

Not related	Any event that does not follow a reasonable temporal sequence from administration of investigational drug AND that is likely to have been produced by the subject's clinical state or other modes of therapy administered to the subject.
Unlikely	Any event that does not follow a reasonable temporal sequence from administration of investigational drug OR that is likely to have been produced by the subject's clinical state or other modes of therapy administered to the subject.
Possibly	Any reaction that follows a reasonable temporal sequence from administration of investigational drug OR that follows a known response pattern to the suspected drug AND that could not be reasonably explained by the known characteristics of the subject's clinical state or other modes of therapy administered to the subject.
Related	Any reaction that follows a reasonable temporal sequence from administration of investigational drug AND that follows a known response pattern to the suspected drug AND that recurs with re-challenge, AND/OR is improved by stopping the drug or reducing the dose.

5.1 ASSESSMENT OF SAFETY

Specification of Safety Variables

Safety assessments will consist of monitoring and reporting adverse events (AEs) and serious adverse events (SAEs) that are considered related to OCR per protocol. This includes all events of death, and any study specific issue of concern.

Adverse Events

An AE is any unfavorable and unintended sign, symptom, or disease temporally associated with the use of an investigational medicinal product (IMP) or other protocol-imposed intervention, regardless of attribution.

This includes the following:

- AEs not previously observed in the subject that emerge during the protocol-specified AE reporting period.
- Complications that occur as a result of protocol-mandated interventions (e.g., invasive procedures such as cardiac catheterizations).
- If applicable, AEs that occur prior to assignment of study treatment associated with medication washout, no treatment run-in, or other protocol-mandated intervention.
- Preexisting medical conditions (other than the condition being studied) judged by the investigator to have worsened in severity or frequency or changed in character during the protocol-specified AE reporting period.

Serious Adverse Events

An AE should be classified as an SAE if any of the following criteria are met:

- It results in death (i.e., the AE actually causes or leads to death).
- It is life threatening (i.e., the AE, in the view of the investigator, places the subject at immediate risk of death. It does not include an AE that, had it occurred in a more severe form, might have caused death.).
- It requires or prolongs inpatient hospitalization.
- It results in persistent or significant disability/incapacity (i.e., the AE results in substantial disruption of the subject's ability to conduct normal life functions).
- It results in a congenital anomaly/birth defect in a neonate/infant born to a mother exposed to the IMP.
- It is considered a significant medical event by the investigator based on medical judgment (e.g., may jeopardize the subject or may require medical/surgical intervention to prevent one of the outcomes listed above).

5.2 METHODS AND TIMING FOR ASSESSING AND RECORDING SAFETY VARIABLES

The investigator is responsible for ensuring that all SAEs that are observed or reported during the study are collected and reported to the appropriate IRB(s) and Genentech, Inc. in accordance with CFR 312.32 (IND Safety Reports).

Adverse Event Reporting Period

The study period during which all AEs and SAEs must be reported begins after informed consent is obtained and ends 30 days following the last administration of study treatment or study discontinuation/termination, whichever is earlier. After this period, investigators should only report SAEs that are attributed to prior study treatment.

Assessment of Adverse Events

All AEs and SAEs whether volunteered by the subject, discovered by study personnel during questioning, or detected through examination, laboratory test, or other means will be reported appropriately. Each reported AE or SAE will be described by its duration (i.e., start and end dates), regulatory seriousness criteria if applicable, suspected relationship to ocrelizumab (see following guidance), and actions taken.

To ensure consistency of AE and SAE causality assessments, investigators should apply the following general guideline:

Yes

There is a plausible temporal relationship between the onset of the AE and administration of ocrelizumab, and the AE cannot be readily explained by the subject's clinical state, intercurrent illness, or concomitant therapies; and/or the AE follows a known pattern of response to ocrelizumab; and/or the AE abates or resolves upon discontinuation of ocrelizumab or dose reduction and, if applicable, reappears upon re-challenge.

No

Evidence exists that the AE has an etiology other than ocrelizumab (e.g., preexisting medical condition, underlying disease, intercurrent illness, or concomitant medication); and/or the AE has no plausible temporal relationship to ocrelizumab administration (e.g., event diagnosed 2 days after first dose of ocrelizumab).

Expected versus unexpected is to be evaluated for SAEs.

Expected adverse events are those adverse events that are listed or characterized in the prescribing information.

Unexpected adverse events are those not listed in the prescribing information or not identified. This includes adverse events for which the specificity or severity is not consistent with the description in the prescribing information. For example, under this definition, hepatic necrosis would be unexpected if the prescribing information only referred to elevated hepatic enzymes or hepatitis.

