Ocrelizumab (OCR), a humanized monoclonal antibody that selectively binds to, and destroys CD20-expressing lymphocytes (B-cell lymphocytes), has demonstrated robust efficacy in reducing relapse rate with a relative reduction of 46% and 47% respectively in OPERA I and II^{xi}. In addition, OCR treatment compared to interferon-β1a therapy led to a significant reduction in contrast enhancing lesions on MRI especially at 24 weeks, 48 weeks, and 96 weeks of treatment with a relative reduction of 94% and 95% respectively. Disability progression at 12 and 24 weeks were also significantly different between both groups with a relative reduction of 40% at 96 weeks. No evidence of disease activity (NEDA) was present in 48% of patients at 96 weeks. The percentage of patients meeting NEDA in the AFFIRM trial was only 37%^{xii}. Also, the number was more impressive for OCR with 72% of patients meeting NEDA when assessed after 24 weeks^{xiii}.

In OPERA I and II, adverse events were the same between the two groups. Not surprisingly, infusion related reactions were more common with 11 patients stopping OCR. Also, in patients receiving OCR, upper respiratory infections and nasopharyngitis were more common. However, unlike NTZ, OCR use has not been associated with the risk of developing PML in patients with MS. Also, to date, there are no reported cases of PML in patients who have received rituximab for the treatment of MS.

The robust therapeutic efficacy of OCR in the phase III pivotal trials, the absence of evidence of PML risk, and the convenience of fewer infusions, makes it an attractive alternative therapy for patients with MS being treated with NTZ, particularly those with the presence of anti-JCV antibodies. However, patients who are JCV negative will likely also be interested in OCR given the potential risk of a false negative to the JCV virus with the reported rate of sero-conversion at 2 to 3 percent per year^{xiv}.

Given the efficacy and safety data demonstrated in these trials, OPERA I and II, we anticipate that physicians and patients with relapsing MS being treated with NTZ independent of the JCV status would be interested in transitioning to OCR.

However, breakthrough disease is well documented in patients electively coming off NTZ to reduce PML risk. Therefore, conducting a study to determine if patients on NTZ regardless of their JCV status can be transitioned to OCR safely without disease progression is vital.

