3.2 RATIONALE FOR STUDY DESIGN

The clinical data from OPERA I and II demonstrated a highly efficacious medication with a significant reduction in relapses, MRI progression, and disability progression. In addition, the data suggest that OCR is well tolerated as only 3.2% of patients withdrew secondary to side effects in OPERA I and 3.8% of patients withdrew in OPERA II. From a safety perspective, no opportunistic infections were seen in the clinical trials, and this includes PML.

NTZ is a highly effective medication for treating patients with relapsing MS. However, despite adequate disease control and JCV status, patients will eventually discontinue secondary to the potential risk of PML^{xv}. Unfortunately, multiple studies have demonstrated an increase in risk of disease progression after switching to another agent after discontinuing NTZ^{xvi, xvii, xviii}. So, given the robust clinical data and safety profile from the pivotal OCR trials, this medication is an attractive option for patients and clinicians.

In this clinical trial, patients will receive the FDA approved dose and frequency of OCR. In the RESTORE trial, NTZ concentrations reached undetectable levels 8 weeks after the last infusion. Also, data from several clinical trials including STRATEGY and SWITCH suggest that a shorter washout period will reduce the risk of disease recurrence^{xix}. Therefore, OCR will be infused at a minimum of 4 weeks after the last dose of NTZ and up until 6 weeks.

Measuring breakthrough disease to date is best evaluated by measuring clinical and radiographic changes. A patient outcome measure, MSIS-29, will help evaluate changes in quality of life after transitioning to OCR.

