- c. If an event is assessed as a "significant medical event," it must be reported as a serious adverse event
- d. Grade 4 and 5 events must be reported as serious adverse events

f. Pregnancy

If a female subject becomes pregnant while receiving ocrelizumab or within 6 months after the last dose of study drug, a report should be completed and expeditiously submitted to the Genentech, Inc. Follow-up to obtain the outcome of the pregnancy

should also occur. Abortion, whether accidental, therapeutic, or spontaneous, should always be classified as serious, and expeditiously reported as an SAE. Similarly, any congenital anomaly/birth defect in a child born to a female subject exposed to the ocrelizumab should be reported as an SAE.

Additional information on any ocrelizumab-exposed pregnancy and infant will be requested by Genentech Drug Safety at specific time points (i.e. after having received the initial report, at the end of the second trimester, 2 weeks after the expected date of delivery, and at 3, 6, and 12 months of the infant's life).

g. Post-Study Adverse Events

The investigator should expeditiously report any SAE occurring after a subject has completed or discontinued study participation if attributed to prior ocrelizumab exposure. If the investigator should become aware of the development of cancer or a congenital anomaly in a subsequently conceived offspring of a female subject who participated in the study, this should be reported as an SAE adequately to Genentech drug Safety and the Sponsor.

h. Case Transmission Verification of Single Case Reports

The Sponsor agrees to complete the Case Transmission verification to ensure that all single case reports have been adequately received by Genentech via the Sponsor emailing Genentech a Quarterly line-listing documenting single case reports sent by the Sponsor to Genentech in the preceding time period.

The periodic line-listing will be exchanged within seven (7) calendar days of the end of the agreed time period. Confirmation of receipt should be received within the time period mutually agreed upon.

If discrepancies are identified, the Sponsor and Genentech will cooperate in resolving the discrepancies. The responsible individuals for each party shall handle the matter on a case-by-case basis until satisfactory resolution. The sponsor shall receive reconciliation guidance documents within the 'Activation Package'.

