Following Case Transmission Verification, single case reports which have not been received by Genentech shall be forwarded by Providence Brain and Spine Institute to Genentech within five (5) calendar days from request by Genentech.

At the end of the study, a final cumulative Case Transmission Verification report will be sent to Genentech.

i. AEs of Special Interest (AESIs)

AESIs are a subset of Events to Monitor (EtMs) of scientific and medical concern specific to OCR, for which ongoing monitoring and rapid communication by the Investigator to the Sponsor is required. Such an event might require further investigation in order to characterize and understand it. Depending on the nature of the event, rapid communication by the trial Sponsor to other parties (e.g., Regulatory Authorities) may also be warranted.

There are no ocrelizumab Events of Special Interest.

Adverse events of special interest for this study include the following:

- Cases of potential drug-induced liver injury that include an elevated ALT or AST in combination with either an elevated bilirubin or clinical jaundice, as defined by Hy's law:
 - Treatment-emergent ALT or AST $> 3 \times$ ULN in combination with total bilirubin $> 2 \times$ ULN
 - Treatment-emergent ALT or AST $> 3 \times$ ULN in combination with clinical jaundice
- Data related to a suspected transmission of an infectious agent by the study drug (STIAMP), as defined below:

Any organism, virus, or infectious particle (e.g., prion protein transmitting transmissible spongiform encephalopathy), pathogenic or non-pathogenic, is considered an infectious agent. A transmission of an infectious agent may be suspected from clinical symptoms or laboratory findings that indicate an infection in a patient exposed to a medicinal product. This term applies only when a contamination of the study drug is suspected

j. Exchange OF Single Case Reports

Providence Brain and Spine Institute will be responsible for collecting all protocol-defined Adverse Events (AEs)/Serious Adverse Events (SAEs), AEs of Special Interest (AESIs), Special Situation Reports (including pregnancy reports) and Product Complaints (with or without an AE) originating from the Study for the Product.

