Investigators must report all the above mentioned single case reports adequately to Genentech and the Sponsor within the timelines described below. The completed MedWatch reporting form should be faxed/mailed immediately upon completion to Genentech and the Sponsor at the following contacts:

All protocol-defined AEs, SAEs, AESIs, Special Situation Reports (including pregnancy reports) and Product Complaints with an AE should be sent to:

**[contact] or
Email: [contact]**

AND

**[contact] (Regulatory) and [contact] (Study Manager) or
Email: [contact] (Regulatory) and CC
[contact] (Study Manager)**

All Product Complaints without an AE should be sent to:

Email: [contact]

AND

**[contact] (Regulatory) and [contact] (Study Manager) or
Email: [contact] (Regulatory) and CC
[contact] (Study Manager)**

It is understood and agreed that the Sponsor will be responsible for the evaluation of AEs/SAEs, AESIs, Special Situation Reports (including pregnancy reports) and Product Complaints (with or without an AE) originating from the study. These single case reports will be exchanged between the parties as outlined below so that regulatory obligations are met.

Serious adverse events (SAEs), AEs of Special Interest (AESIs), pregnancy reports, other Special Situation Reports and Product Complaints (with or without an AE), where the patient has been exposed to the Genentech Product (OCR), will be sent on a MedWatch form to Genentech Drug Safety and to the Sponsor. Transmission of these reports (initial and follow-up) will be either electronically or by fax and within the timelines specified below:

- **Serious Adverse Drug Reactions (SADRs)**

Serious AE reports that are related to OCR shall be transmitted to Genentech and the Sponsor within fifteen (15) calendar days of the awareness date.

- **Other SAEs**

Serious AE reports that are unrelated to OCR shall be transmitted to Genentech and the Sponsor within thirty (30) calendar days of the awareness date.

- **AESIs**

AESIs shall be forwarded to Genentech and the Sponsor within fifteen (15) calendar days of the awareness date.

- **Special Situation Reports**

Pregnancy reports

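### The reporting period in 5.2 can close while a patient who stopped OCR is still attending study visits, and an SAE attributed to prior NTZ is then not reportable under that rule

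*Combined protocol and SAP*

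**What the plan says.** The Introduction gives the motive for the trial: finding out whether patients on NTZ "can be transitioned to OCR safely without disease progression is vital". The formal secondary objective (2.2) is the safety and tolerability of OCR in patients who previously had NTZ.

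On causality, 5.2 has each event described by its "suspected relationship to ocrelizumab (see following guidance), and actions taken". The answer No is open where "Evidence exists that the AE has an etiology other than ocrelizumab". Section 5 has a separate four-level scale, also about the study drug. Neither scale names NTZ.

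On timing, 5.2 starts AE and SAE reporting at consent and stops it 30 days after the last study treatment or study discontinuation, taking the earlier. Then: "After this period, investigators should only report SAEs that are attributed to prior study treatment". Section 5.3 g sets the matching rule for patients who have left the study: an SAE is to be reported "if attributed to prior ocrelizumab exposure".

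Three other places point the other way:
- The first sentence of 5.2 makes the investigator answerable for every SAE that comes to light while the study runs.
- Section 3.1 has patients who stop OCR but stay on complete every remaining visit item except dosing and pregnancy testing.
- Appendix A has AEs monitored and recorded at each visit after screening.

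**The concern.** In a switch study, a serious event after the change of drug may be due to OCR, to NTZ carried over, or to the sequence. The data can separate these only if someone asks about NTZ, and they can include late events only if collection stays open while the patient is followed.

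Under 5.2 the clock runs from the last OCR dose and not from the patient's last contact with the trial. A patient who stops OCR early and stays is examined for months after the stated period has ended. During those months the rule admits an SAE only if it is attributed to OCR. An SAE put down to NTZ, or to anything else, is excluded, and non-serious AEs are excluded altogether.

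The plan aims at five centres. A site that follows the window in 5.2 and a site that follows Appendix A would collect different events from similar patients. The AE and SAE counts in 3.3.2 would then not have one definition.

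**Working it through.** The plan states no figure for this point, so the check is date arithmetic on its own rules.

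Inputs:
- First OCR dose 28 to 42 days after the last NTZ dose (3.1, 4.3).
- OCR on Day 0, Day 14, Day 168 and Day 336, nominal days (4.5.1).
- Period ends 30 days after the last OCR dose (5.2). For a patient who stays under observation, study discontinuation comes later, so the dose date governs.
- Last scheduled visit Day 336 (4.5.1).

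Formulas: closure = last dose day + 30. Days since NTZ = closure + 28 to closure + 42. Follow-up left = 336 − closure.

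| Last OCR dose | Period closes | Days since last NTZ | Days left to Day 336 | Visits still due |
|---|---|---|---|---|
| Day 0 | 0 + 30 = 30 | 58 to 72 | 336 − 30 = 306 | Months 3, 6, 9, 12 |
| Day 14 | 14 + 30 = 44 | 72 to 86 | 336 − 44 = 292 | Months 3, 6, 9, 12 |
| Day 168 | 168 + 30 = 198 | 226 to 240 | 336 − 198 = 138 | Months 9, 12 |
| Day 336 | 336 + 30 = 366 | 394 to 408 | none | none |

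The rule also admits a second reading, in which the period ends on the day of study discontinuation itself. That would not change the first three rows for patients who stay, but it could close the period sooner for a patient who withdraws.

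Overlap of the two drugs: 3.2 reports that "NTZ concentrations reached undetectable levels 8 weeks after the last infusion", which is 56 days. OCR starts at day 28 to 42 after NTZ, so by this figure NTZ is still detectable for the first 56 − 42 = 14 to 56 − 28 = 28 days on OCR. A question about NTZ is therefore not idle. In every row the period closes after day 56, but detectability does not say how late an NTZ-related event can appear, and the documents give no such interval.

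Scale, for illustration only: the Introduction cites a progressive multifocal leukoencephalopathy (PML) risk of 4.22 per 1000. Applied in full to 50 patients it gives 50 × 0.00422 = 0.21 expected cases, and 1 − (1 − 0.00422)^50 = 0.19 as the chance of at least one. The documents give no risk after switching, so the range is 0 to 0.21. It covers all 50 patients and is not an estimate of cases lost through the gap.

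**The case against.** The best defence is that little is lost. Section 5 records every AE whatever its relationship to the drug. Section 5.3 j still covers attribution elsewhere: "Serious AE reports that are unrelated to OCR shall be transmitted to Genentech and the Sponsor". The outcomes in 3.3.2 and 3.3.3 count AEs, SAEs and infections with no attribution filter. Section 5.4 asks the MedWatch reporter about each suspect medication. Completers are covered for more than a year after NTZ. OCR is the study treatment, so attribution to OCR matches the objective in 2.2. All of this stands for events inside the period. None of it settles what happens after the period closes on a patient still being seen, and the MedWatch item applies only once a report is made.

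A reader might go further and infer three things that the documents do not support.

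- That NTZ events are bound to be coded unrelated. In the section 5 scale, Not related also requires the absence of a reasonable temporal sequence. In 5.2, a known OCR pattern alone can give Yes.
- That the safety conclusion is too favourable overall. Events inside the period are counted whatever their code. Section 4.9.4 lists relationship to drug and to therapy separately, although it defines neither.
- That suspected PML triggers no rapid report, because the special-interest list omits it and says "There are no ocrelizumab Events of Special Interest". PML would normally meet the SAE criteria in 5.1, including the investigator-judgment criterion for a suspected case. Section 5 asks for SAEs within 24 hours, whereas special-interest events have 15 days in 5.3 j.

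**Conclusion.** The point holds in a limited form. Section 5.2 contradicts itself, 3.1 and Appendix A about patients who stop OCR and remain under observation. Under its stated window, 138 to 306 days of scheduled follow-up lie outside reporting for SAEs not attributed to OCR, depending on when OCR stopped. Separately, no causality scale asks about NTZ, so carry-over cannot be told apart from OCR effects in the tables.

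This rests on reading study treatment in 5.2 as OCR, which 4.3 and 5.3 g support, and on nominal visit days. The effect is confined to early stoppers and to events after the period closes. How many patients will stop and stay, and how many events would be missed, cannot be computed from the documents. Sample size, significance level and the primary endpoint are untouched.

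**What to change.** 1. In 5.2, reconcile the passages so that all AEs and SAEs are reported, whatever the attribution, until the later of the end of the patient's study follow-up (including observation off OCR) and 30 days after the last OCR dose. Bring the scope sentence in 5.1, which speaks only of OCR-related events, into line with section 5 and 5.3 j.
2. Add one causality item to the case report form for relationship to prior NTZ, consistent with what 5.4 already asks on MedWatch. Tabulate it in 4.9.4 beside relationship to OCR.
3. In 5.2 and 5.3 g, extend the rule for later SAEs to those attributed to prior NTZ as well as OCR.

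The cost is one form field, some protocol wording and a few more reported events. No visit or procedure is added. Listing PML as an event of special interest, or defining a composite category of switch-related events, is optional and adds little once these three changes are made.

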3.3.3 Ancillary Safety Outcome Measures

- Number and type of infusion related reactions based on dose including the severity of the reactions
- Number of and type of infections during the trial.

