Although ocrelizumab may be administered on an outpatient basis, patients may be hospitalized for observation at the discretion of the investigator. Ocrelizumab infusions should always be administered in a hospital or clinic environment under close supervision of the investigator or a medically qualified staff member.

See section 3.4 for recommended pre-medications and recommended medications to treat IRRs. For the 300-mg dose, each ocrelizumab infusion should be given as an IV infusion over approximately 150 minutes (2.5 hours). For the 600-mg dose, each ocrelizumab infusion should be given as an IV infusion over approximately 215 minutes (3.5 hours). Since transient hypotension may occur during ocrelizumab infusion, the investigator may wish to withhold anti-hypertensive medications 12 hours prior to ocrelizumab infusion.

Ocrelizumab must not be administered as an IV push or bolus. Well-adjusted infusion pumps should be used to control the infusion rate, and ocrelizumab should be infused through a dedicated line. It is important not to use evacuated glass containers (to prepare the infusion), which require vented administration sets, because this causes foaming as air bubbles pass through the solution.

After completion of the infusion, the IV cannula should remain in situ for at least 1 hour to allow for administration of drugs intravenously, if necessary, in the event of a delayed reaction. If no adverse events occur during this period of time, the IV cannula may be removed and the patient may be discharged.

See the OCR prescribing information dated 11/2018 for detailed instructions on drug preparation, storage, and administration.

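### The only example of implausible timing in Section 5.2, an unspecified event two days after the first dose, contradicts the guide's own criteria, so early events could be coded unrelated or coded inconsistently

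*Combined protocol and SAP*

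**What the plan says.** Section 5.2 (Assessment of Adverse Events) introduces its causality guide with "To ensure consistency of AE and SAE causality assessments, investigators should apply the following general guideline". Each branch is a list of limbs joined by and/or, so one limb is enough.

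- **No branch.** Either there is evidence of another cause, or "the AE has no plausible temporal relationship to ocrelizumab administration (e.g., event diagnosed 2 days after first dose of ocrelizumab". This is the guide's only illustration of timing, and it does not restrict the kind of event.
- **Yes branch.** The onset has a plausible relation in time to dosing and the event is not readily explained otherwise; "and/or the AE follows a known pattern of response to ocrelizumab"; or the event improves when the drug is stopped or reduced and, where tested, returns on re-exposure.

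Section 5 (Relationship to Study Drug) has a separate four-level scale with no such example. Its lowest level, Not related, begins "Any event that does not follow a reasonable temporal sequence from administration of investigational drug" and also requires a likely other cause. The level Possibly begins "Any reaction that follows a reasonable temporal sequence from administration of investigational drug", with a known response pattern as the alternative, and requires that the patient's condition or other treatment does not reasonably explain the event.

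The code is used in four places. Section 4.9.4 summarises relationship to drug. Section 5.1 words the safety assessment around events considered related. Section 5.3 j allows 15 calendar days for related serious events, while "Serious AE reports that are unrelated to OCR shall be transmitted to Genentech and the Sponsor within thirty (30) calendar days". Section 6.3 ties prompt IRB notification to events that are serious, unexpected and thought at least possibly due to the drug.

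**The concern.** Two days after an infusion is close in time by any ordinary reading, and closeness in time normally counts towards a drug relationship. The example makes it a reason against one. Because the limb suffices alone, a site following it literally needs no alternative cause to record No. The error also runs in one direction, towards unrelated, just after first exposure.

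Safety and tolerability are a secondary objective (Section 2.2). The study has no control arm, so there is no comparator rate against which misattribution would show up. The investigator's causality call therefore carries more weight in the safety summary than it would in a controlled trial.

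**Working it through.** There is no figure to reproduce, so the check is textual. Take three events, each first diagnosed two days after the first dose, and apply each instrument as written. For the first two, assume no other cause is evident.

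| Event | 5.2 Yes branch | 5.2 No branch | Section 5 scale |
|---|---|---|---|
| Infusion reaction or upper respiratory infection (Section 1 reports both as more common on ocrelizumab) | Met, by known pattern | Met, by the example | At least Possibly |
| Event with no known pattern | Met on timing only if the example is disregarded | Met, by the example | At least Possibly, if Day 2 is a reasonable sequence |
| Condition that could not develop in two days, such as a malignancy | Not met | Met, and properly so | Unlikely, or Not related if another cause is likely |

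1. In the first row the event satisfies both branches. No precedence rule exists, so the code is indeterminate and two sites could record different answers while both follow the text.
2. In the second row the known-pattern limb gives no protection. The limb on improvement after stopping can be judged only later. The literal answer at diagnosis is No, while the Section 5 scale gives at least Possibly.
3. Only in the third row does the example do what it was presumably meant to do, and the text does not confine it to that case.

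**Scope.** The example refers to the first dose only, which is one of four scheduled infusions (Day 0, Day 14, Month 6, Month 12). It does not describe a reaction on the day of infusion. It turns on the date of diagnosis, whereas the timing limb of the Yes branch turns on onset. An event that began earlier but was diagnosed on Day 2 therefore also falls within the literal wording.

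**What moves with the code.** The Section 4.9.4 summary changes directly. Under Section 5.3 j the nominal transmission limit for a serious event moves from 15 to 30 calendar days, a difference of 30 − 15 = 15 days. Section 6.3 is affected less directly, because it uses graded wording rather than the Yes/No code.

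**What does not move.** Section 5 requires every adverse event to be recorded whatever its relationship, and every serious event to go to Genentech and the sponsor's regulatory office within 24 hours. Section 5.2 itself makes the investigator responsible for reporting all serious events to the IRB(s). The counts in Section 3.3.3 are not conditioned on causality.

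**The case against.** The best defence is that the parenthesis is an illustration inside a general guideline, not a rule. The criterion itself is implausible timing, and an event with plausible timing does not meet it. The word for diagnosis, set against onset in the Yes branch, suggests the authors had in mind a condition found too soon to have been caused by the drug. Infusion reactions and respiratory infections can be coded Yes through the known-pattern limb on any day. The Section 6.3 route also requires the event to be unexpected, and Section 3.4 shows that infusion reactions are already in the prescribing information.

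Most of this stands, and it rules out several stronger inferences.

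- A reader might infer that early infusion reactions and infections will be coded unrelated. The documents support only that they could be.
- A reader might take Section 4.3.1's phrase "in the event of a delayed reaction" as proof that the protocol expects Day 2 reactions. That sentence explains why the cannula stays in for at least an hour after the infusion, so it concerns the same day.
- A reader might expect the outcome "Number of and type of infections during the trial" to be undercounted. It counts all infections, whatever the causality code.
- A reader might conclude that a serious Day 2 event would reach Genentech 15 days later. The 24-hour rule in Section 5 applies regardless of causality. Its conflict with Section 5.3 j is a separate matter.

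The defence does not remove the defect. The benign reading has to be supplied by the reader, in a guide whose stated purpose is uniform assessment. The known-pattern limb does not help an event with no known pattern. Such an event is also more likely to be unexpected in the sense of Section 6.3.

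**Conclusion.** The concern holds in limited form. Section 5.2 contains a wrong, or at best badly under-specified, example in an instruction that sites are told to apply. It conflicts with the guide's own Yes branch and with the Section 5 scale. A Day 2 event after the first dose could be coded unrelated, or coded inconsistently across centres.

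The consequence is confined to attribution: a descriptive summary, and reporting routes that other all-event duties partly backstop. No efficacy result, adverse event count or infusion-reaction count depends on it.

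The number of events affected cannot be derived from the documents. Every patient who starts ocrelizumab (target 50) passes through that day once, but this describes exposure to the wording and is not an effect size. The conclusion assumes that at least some sites would read the example literally, and that no separate completion instructions correct it; the documents show none. It should be corrected, because the error is plain on the page and the remedy is small, but it does not threaten the study's main conclusions.

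**What to change.** In Section 5.2:

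1. Delete the parenthesis, or replace the unspecified event with a condition that could not develop in two days, for example a malignancy.
2. Add that closeness in time to an infusion is never by itself a reason for No.
3. State which branch prevails when an event meets both.

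Carry the same text into any adverse event completion instructions given to sites. The overlap of two causality scales (Sections 5 and 5.2), and the 24-hour against 15- and 30-day time limits (Sections 5 and 5.3 j), should be reconciled at the same time as separate items.

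The cost is one phrase and two added sentences, in an amendment that needs IRB approval under Section 3.5. The downside is that slightly more early events may be coded related, which is the cautious direction.
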